7.2 Rationale for the Study

This study is being performed to evaluate the efficacy and safety of different dose levels and dosing regimens of SCY-078 as compared to fluconazole in adult female patients 18 years and older with moderate to severe AVVC.

Rationale for Study Indication and Population

Considering the properties of SCY-078 as a potent antifungal compound, with fungicidal activity against *Candida* spp., it will represent an important non-azole alternative treatment for subjects suffering from AVVC.

Subjects with moderate to severe AVVC are intended for this study to facilitate the identification of a clinically meaningful effect of SCY-078 with a limited sample size.

Rationale for Selected Dose Levels and Dosing Regimens

The SCY-078 dose levels and dosing regimens selected for this study (750 mg QD for 1 day, 300 mg twice daily [BID] for 1 day [total daily dose of 600 mg], 450 mg BID for 1 day [total daily

dose of 900 mg], 150 mg BID for 3 days [total daily dose of 300 mg] or 300 mg BID for 3 days [total daily dose of 600 mg]) are in the range of doses that have been well tolerated in Phase 1 investigations. Since the estimated effective exposure of SCY-078 for vulvovaginal candidiasis has not been determined, this study will contribute to a better understanding of the exposures that may be associated with clinical efficacy for this indication to guide further investigations.

The dose selected for the active comparator of this study (fluconazole) is one single oral dose of 150 mg, which is the recommended and approved dose for this indication.

Rationale for Study Endpoints

The primary endpoint for the study is clinical cure (complete resolution of signs and symptoms) of the acute symptomatic episode at the test-of-cure (TOC) visit on Day 10 (± 2), which is in line with current regulatory guidance for this condition.⁹ The secondary efficacy endpoints will include mycological eradication (negative fungal culture) at TOC, a composite endpoint of both clinical cure and mycological eradication at the TOC and FU visits, continued clinical response (continued absence of signs and symptoms) at the Follow-up (FU) visit on Day 25 (+4), and time to resolution of signs and symptoms, which are also in line with current guidelines. The safety and tolerability of SCY-078 will also be evaluated as secondary objectives. Other objectives of the study will be to explore the efficacy of SCY-078 based on KOH testing at the TOC visit and based on additional clinical outcomes (clinical response regardless of clinical outcome at TOC) at the FU visit, to explore the prevalence of different *Candida* species, to explore the *in vitro* activity of SCY-078 against baseline *Candida* spp. isolates, to explore clinical and mycological outcomes by *Candida* species, and to evaluate the PK of SCY-078.

Rationale for Study Design

This trial is being conducted as a double-blind, double-dummy study. This design is considered an appropriate design for this indication and phase of investigation, and will use matching SCY-078 and fluconazole placebo to accommodate the differences in the dosing regimens and formulations of SCY-078 and the comparator (fluconazole).

The data generated from this study will provide an initial characterization of the safety and tolerability of SCY-078 in subjects with AVVC, and will provide an initial indication of the most effective dosing regimen with efficacy of SCY-078 in this condition. Results from this study will guide subsequent phases of development for this indication.

8.0 Study Objectives

8.1 Primary Objectives

- To identify the recommended dose of oral SCY-078 in subjects with moderate to severe AVVC by comparing the efficacy of different dose levels and dosing regimens of oral SCY-078

8.2 Secondary Objectives

- To evaluate the efficacy of oral SCY-078 in subjects with AVVC based on mycological and clinical outcomes
- To evaluate the safety and tolerability of different dose levels and dosing regimens of oral SCY-078 in subjects with AVVC

8.3 Exploratory Objectives

- To explore the efficacy of SCY-078 in subjects with AVVC based on potassium hydroxide (KOH) testing at the TOC visit
- To explore the efficacy of SCY-078 in subjects with AVVC based on additional clinical outcomes
- To explore the prevalence of *Candida* species among subjects with AVVC
- To explore the *in vitro* activity of SCY-078 against baseline *Candida* spp. isolates
- To explore clinical and mycological outcomes by *Candida* species
- To evaluate the PK of SCY-078 after oral administration of different dose levels and dosing regimens of SCY-078 in subjects with AVVC

9.0 Study Endpoints

9.1 Primary Endpoints

- Efficacy as measured by the percentage of subjects with clinical cure (complete resolution of signs and symptoms) at the TOC visit

9.2 Secondary Endpoints

Efficacy as measured by:

- The percentage of subjects with mycological eradication (negative fungal culture) at the TOC visit

- The percentage of subjects with both clinical cure and mycological eradication at the TOC and FU visits.
- The percentage of subjects with continued clinical response (continued absence of signs and symptoms) at the Follow-up (FU) visit.
- The time to resolution of signs and symptoms after initiation of study drug

Safety and tolerability as measured by:

- AEs, treatment discontinuations, vital signs, physical examination and safety laboratory tests

9.3 Exploratory Endpoints

- Percentage of subjects with a negative KOH test at the TOC visit
- Percentage of subjects who are free of signs and symptoms at the FU visit
- Percentage of subjects by *Candida* species infection at Baseline
- Percentage of isolates susceptible to SCY-078 and fluconazole
- Percentage of subjects with clinical cure (complete resolution of signs and symptoms) at TOC by *Candida* species
- Percentage of subjects with mycological eradication (negative fungal culture) at TOC by *Candida* species
- Determination of the PK parameters (C_{max} and AUC) for each dosing regimen and evaluation of the dose/exposure relationship relative to clinical outcome

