SCY-078 has been evaluated against >1200 *Candida* isolates, including all clinically relevant species, more than 300 *C. glabrata* isolates and 16 *C. auris* isolates. These *in vitro* studies have demonstrated the broad spectrum of anti-*Candida* activity of SCY-078. Additionally, SCY-078 demonstrated *in vitro* activity against pre-formed biofilms, which is a relevant feature when addressing catheter-related *Candida* infections. Studies conducted with azole- and echinocandin-resistant strains have shown that SCY-078 retains activity (i.e., no significant change in minimum inhibitory concentration when compared to wild type) against >90% of azole-resistant strains and >70% of *Candida* strains with *FKS* mutations commonly associated with echinocandin resistance. Interestingly, although SCY-078 and the echinocandins share a similar mechanism of action (β -[1,3]-D-glucan synthesis inhibition), their clearly different molecular structure provides them with some differentiating characteristics in terms of microbiological activity.

SCY-078 was evaluated *in vitro* against >170 clinical isolates of echinocandin-resistant strains of *Candida* spp., >95% of which contained mutations in the *FKS* gene. Overall, SCY-078 was active against the majority of the echinocandin-resistant strains tested. Significantly, SCY-078 was active against approximately 70% of the isolates containing the most commonly reported *FKS* mutation associated with echinocandin resistance in *C. glabrata* (S663P in *FKS2* and S645P in *FKS1*). Selection of SCY-078 resistance *in vitro* occurs at a low frequency. A deletion at position F659 in *FKS2* of *C. glabrata* was the predominant mutation observed in these studies; notably, SCY-078 did not select for mutations at positions S663 or S645. These results suggest that SCY-078 inhibits glucan synthase in a manner different from that of echinocandins.

The *in vitro* studies also included several multidrug-resistant isolates. Consistent with the data described above, SCY-078 was active against >70% of these isolates. SCY-078 has also demonstrated a potent activity against life-threatening and multi-drug-resistant *C. auris* strains

over 16 different *C. auris* isolates, at concentrations indicative of potential clinically relevant effect.⁷ *C. auris* has been recently highlighted as a clinical alert by the CDC because of the global emergence of this fungal infection with limited therapeutic options and high mortality.

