Activity against *Aspergillus* spp.

The *in vitro* activity of SCY-078 has been evaluated against >150 clinical *Aspergillus* isolates, including most clinically relevant species and azole-resistant strains. The results demonstrated potent activity of SCY-078 against all of the strains tested.

Murine models of invasive fungal infections

The antifungal efficacy of SCY-078 has been evaluated in several murine models of disseminated candidiasis and aspergillosis. In a disseminated *C. albicans* model, SCY-078 was more active than fluconazole at all doses. Murine models of SCY-078 in disseminated candidiasis caused by *C. glabrata* and *C. tropicalis* indicated activity across multiple *Candida* species. The SCY-078 area under the concentration-time curve (AUC) in plasma necessary to achieve target efficacy in these models was estimated to be $15.4 \pm 2.2 \mu\text{M}\cdot\text{hr}$.

Nonclinical experience

Toxicology studies in rats and dogs have been conducted with SCY-078 following oral administration for up to 90 days. The results from the non-clinical safety program are supportive of the doses and treatment duration intended in this study.

The *in vitro* studies indicated that SCY-078 metabolism was predominantly oxidative, with cytochrome P450 (CYP) 3A being the primary enzyme involved in its oxidative metabolism. Strong inhibitors of CYP3A would be expected to increase plasma levels of SCY-078; therefore, the concurrent administration of SCY-078 with such inhibitors is prohibited.

Clinical experience

To date, over 300 subjects and patients have received either oral or IV formulations of SCY-078 in Phase 1 and Phase 2 studies.

SCY-078 was generally well tolerated following single oral doses of up to 1600 mg and multiple oral doses of up to 800 mg/day for 28 consecutive days in Phase 1 studies. Reported adverse events (AEs) after oral administration have been generally transient and primarily mild to moderate in intensity. The most frequently reported AEs have been mild gastrointestinal events (nausea, vomiting, diarrhea and abdominal pain).

A Phase 2 study of oral SCY-078 as step-down therapy from IV echinocandin in patients with invasive candidiasis has been completed. Following three to ten days of IV echinocandin therapy, 21 patients received either SCY-078 or fluconazole. SCY-078 was well tolerated, with an AE profile typical of this population and comparable to the SOC. The results from this study also

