14.9 Vulvovaginal Samples for KOH and Fungal Culture

At Screening, a vulvovaginal specimen will be obtained for direct microscopic examination with 10% KOH. Subjects must have a positive KOH test at Screening to be randomized to one of the study treatment groups. The Screening KOH will be assessed at the site by the investigator or designee. A vaginal sample will also be obtained at Screening for fungal culture and species identification by the central laboratory and for susceptibility testing against SCY-078, fluconazole and additional antifungal agents. Central susceptibility testing will be done as per CLSI M27-A3 guidelines. An additional vulvovaginal specimen will be collected at the TOC and FU visits for local KOH testing and for fungal culture by the central laboratory for treatment outcome assessment. In addition, susceptibility testing will be done at the central laboratory for all positive cultures for *Candida* spp. Vulvovaginal samples may also be taken at unscheduled visits, if needed.

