11.8.3 Exploratory Efficacy Endpoints

The exploratory efficacy endpoints include the following:

- Percentage of subjects with a negative KOH test at the TOC visit
- Percentage of subjects who are free of signs and symptoms at the FU visit
- Percentage of subjects by *Candida* species infection at Baseline
- Percentage of isolates susceptible to SCY-078 and fluconazole at the TOC and FU visits
- Percentage of subjects with clinical cure at TOC by *Candida* species at Baseline
- Percentage of subjects with mycological eradication at TOC by *Candida* species at Baseline

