11.9.3 Exploratory Efficacy Analyses

The exploratory efficacy analyses will be conducted using the mITT and PP populations, following the same methods/tests as described for the primary and secondary endpoints.

For the subgroup analyses by *Candida* species, only descriptive statistics will be provided; no statistical testing will be performed due to possible small sample size.

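### The exploratory endpoint on isolates susceptible to SCY-078 and fluconazole has no MIC cut-off for either drug, and the SAP as written would test it between arms on post-treatment isolates only

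*Protocol*

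**What the plan says.** The protocol's exploratory endpoint is "Percentage of isolates susceptible to SCY-078 and fluconazole" (Protocol 9.3; the synopsis, 10.1.2 and 18.7.1 carry the same endpoint). The SAP version adds timepoints: "Percentage of isolates susceptible to SCY-078 and fluconazole at the TOC and FU visits" (SAP 11.8.3).

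On method, Protocol 14.9 says "Central susceptibility testing will be done as per CLSI M27-A3 guidelines", and that positive *Candida* cultures at TOC and FU are tested as well as the screening isolate.

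On analysis, SAP 11.9.3 handles exploratory endpoints in the mITT and PP populations, "following the same methods/tests as described for the primary and secondary endpoints". Its one exemption from testing is for subgroup analyses by *Candida* species.

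The matching objective (Protocol 8.3, SAP section 2) is to explore in vitro activity of SCY-078 against isolates taken at baseline.

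**The concern.** A percentage susceptible is a count of isolates on one side of a threshold. Without the threshold the endpoint is not defined: two analysts with the same MICs could report different percentages and both follow the plan. If the plan is final and silent, a cut-off supplied later also meets SAP section 12, which gives analyses not specified in the SAP unblinded, exploratory status.

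The second issue is the test. After treatment, an isolate exists only if the subject is culture-positive, and culture status is itself an outcome of treatment. A between-arm test at TOC or FU therefore compares subsets that treatment has helped to select, not the randomised groups. The unit is the isolate, while the tests inherited from the primary endpoint are built for one observation per subject.

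The third issue is that the SAP's two timepoints leave out baseline, the only one that the objective names.

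**Working it through.** The documents state no susceptibility figure, so there is nothing to reproduce. The check is a reading of the text, followed by an illustration of sensitivity.

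**1. Is a cut-off given anywhere?** These are the places where one could be:

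- Protocol 9.3 and SAP 11.8.3 give the endpoint only, with no threshold for SCY-078 or fluconazole.
- Protocol 14.9 names a testing method. It does not say that the method supplies a breakpoint for either drug, and this cannot be checked from the documents.
- Protocol 7.1 describes retained activity as "no significant change in minimum inhibitory concentration when compared to wild type". It also reports shares of resistant isolates against which SCY-078 was active. It gives no MIC value and no link to this endpoint.
- Protocol 7.1 also gives a plasma exposure target from mouse models of disseminated infection; the AUC "necessary to achieve target efficacy in these models was estimated to be" 15.4 ± 2.2 µM·hr. That is an exposure in another disease, not an MIC cut-off.
- Protocol 7.2 says that "the estimated effective exposure of SCY-078 for vulvovaginal candidiasis has not been determined".
- The SAP contains no derivation rule for classifying an isolate.

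Result: no cut-off and no source for one, for either drug.

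**2. Which tests apply as written?** SAP 11.9.3 refers back to the primary and secondary methods. For a binary endpoint these are, in SAP 11.9.1, a Cochran-Mantel-Haenszel row mean scores test stratified by site and pairwise Fisher's exact tests against fluconazole. The by-species exemption does not reach the susceptibility endpoint, which is not a subgroup analysis.

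**3. On which isolates?** Combining SAP 11.8.3 (TOC and FU) with Protocol 14.9 (susceptibility testing of positive cultures), the tested set is isolates from subjects who are culture-positive after treatment. No rule says how many isolates a subject may contribute.

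**4. How far could the percentage move?** The documents contain no MIC data, so this rests on an assumption: log2 MIC is normal, with SD 1 or 1.5 doubling dilutions. With the cut-off k dilutions above the median, percentage susceptible = 100 × Φ(k / SD).

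| SD | k = 0 | k = 1 | k = 2 | k = 3 |
|---|---|---|---|---|
| 1 | 50.0 | 84.1 | 97.7 | 99.9 |
| 1.5 | 50.0 | 74.8 | 90.9 | 97.7 |

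The change for a one-dilution shift is:

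- Median to +1: 84.1 − 50.0 = 34.1 points (SD 1); 74.8 − 50.0 = 24.8 points (SD 1.5).
- +1 to +2: 97.7 − 84.1 = 13.6 points; 90.9 − 74.8 = 16.1 points.
- +2 to +3: 99.9 − 97.7 = 2.2 points; 97.7 − 90.9 = 6.8 points.

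The first step is the steepest part of the curve. Nothing in the documents fixes where the cut-off would lie.

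**The case against.** The strongest reply is that little hangs on this. It is one of seven exploratory endpoints in Protocol 9.3, no primary or secondary analysis uses it, and both documents say that the study is not powered for formal comparisons. That stands, and it limits the weight of the point.

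Several stronger readings are tempting, but the documents do not support them:

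- *The cut-off will be chosen after MICs and outcomes are known.* This would be inferred from silence. Under SAP section 5 the study is unblinded only after data review and database closure, so a cut-off can still be fixed blind. A laboratory manual exists (Protocol 14.8) and was not available here; it might hold one.
- *No cut-off could be set in advance because effective exposure is unknown.* The statement in Protocol 7.2 rules out only an exposure-based cut-off. One based on the wild-type MIC distribution needs no exposure target and could be prespecified.
- *The percentage is uncertain by 25 to 34 points.* That is the case at the median. Protocol 7.1 reports activity retained against more than 90% of azole-resistant strains. If the cut-off sits well above the median, the shift is a few points.
- *The SCY-078 and fluconazole percentages would not be comparable.* Neither document plans to compare them.

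It is also fair to say that SAP 11.9.3 is a catch-all sentence. Taken literally, it would test baseline species prevalence too. So the planned test may be loose wording rather than intent. But the sentence lists its exemption, and this endpoint is not in it. The text as it stands calls for the test, and one added clause settles it.

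**Conclusion.** The point holds. The endpoint is undefined for both drugs, not for SCY-078 alone. As written, it is also tested between arms at the isolate level on a set of isolates that treatment has shaped, at timepoints that leave out the baseline isolates named in the objective.

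Its reach is limited to this exploratory endpoint; the primary and secondary conclusions do not change. Under the normal assumption for log2 MIC with SD 1 to 1.5 dilutions, a one-dilution choice of cut-off is worth 25 to 34 points at the median and about 2 to 7 points between +2 and +3 dilutions. Those figures show how the result behaves. They do not predict this trial's MICs.

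This is more than a missing detail that a laboratory footnote would cure. Naming a cut-off would define the percentage, but would leave the post-treatment test and the missing baseline timepoint in place.

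**What to change.** Before unblinding:

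- In SAP 11.8.3, report the SCY-078 MIC distribution by species for baseline isolates: range, MIC50, MIC90 and cumulative percentage at each dilution. Give the same summary descriptively at TOC and FU. No threshold is needed, and a reader can apply any later cut-off to the cumulative column.
- State the counting rule: one isolate per species per subject per visit.
- Give a percentage susceptible, for either drug, only where the cut-off and its source are named in advance.
- Add this endpoint to the exemption in SAP 11.9.3, so that it is descriptive only.
- Record the change in SAP section 12, since the protocol lists a percentage and Protocol 18.7.2 assigns Fisher's exact test to categorical endpoints generally.

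The cost is a few lines of SAP text and one changed exploratory table. A headline percentage for SCY-078 may be dropped if no cut-off can be named. Samples already go to the central laboratory for susceptibility testing, so no new sampling is needed, assuming that the laboratory reports MICs and not only categories. Some by-species cells will be small, which is acceptable in a descriptive table.

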10.0 Study Design

10.1 Overall Description of the Study

This is a multicenter, randomized, double-blind, double-dummy, active-controlled, dose-finding study to compare the efficacy, safety and tolerability of oral SCY-078 compared to oral fluconazole in adult female subjects 18 years and older with moderate to severe AVVC. Approximately 180 eligible subjects (30 subjects per treatment group) will be enrolled and randomized into the study.

The primary objective of this study is to identify the recommended dose of oral SCY-078 in subjects with moderate to severe AVVC by comparing the efficacy of different dose levels and dosing regimens of SCY-078.

The study will consist of a Screening visit, a Baseline visit on Day 1, a study visit on Day 3 (which will consist of an on-site visit for PK sampling for a subset of subjects and a phone contact for all other subjects), a TOC visit (which will include PK sampling for the PK Subset of subjects) on Day 10 (± 2) and a FU visit on Day 25 (+4). The Screening and Baseline visits may be combined. Efficacy, safety, tolerability and PK assessments will be conducted for the study.

Efficacy will be determined primarily by the percentage of subjects with clinical cure (complete resolution of signs and symptoms) at the TOC visit. Secondary efficacy endpoints will include mycological eradication (negative fungal culture) at the TOC visit, a composite endpoint of both clinical cure and mycological eradication at the TOC and FU visits, continued clinical response (continued absence of signs and symptoms) at the FU visit, and the time to resolution of signs and symptoms after initiation of study drug. Other efficacy endpoints will also be explored. Safety and tolerability will be evaluated throughout the study, including the following parameters: physical exam, vital signs, AEs, treatment discontinuations and safety laboratory tests. A subset of approximately 60 subjects will also undergo blood sampling for PK analyses of SCY-078 in plasma.

A summary description of the study visits and assessments is provided below. A schematic of the study design is available in [Section 6.0](#). Detailed descriptions of study treatments and procedures are provided in [Section 12.0](#) and [Section 14.0](#), respectively.

10.1.1 Study Visits

Screening (Day -1)

Consenting subjects who are experiencing vulvovaginal symptoms at Screening will be evaluated by the investigator, who will obtain a vaginal sample for local KOH testing and for fungal culture and species identification by the central laboratory. Susceptibility testing will be done at the central laboratory for all positive cultures for *Candida* spp. Additional vaginal samples will be collected, if clinically indicated, to be examined for the presence of other pathogens (e.g., causative agents for bacterial vaginosis, *Trichomonas*, *Herpes* virus, *N. gonorrhoea*, *Chlamydia*, human papillomavirus or other mixed infections) by a qualified laboratory (central or local laboratory) and for the determination of vaginal pH by the investigator. The investigators and the subjects will rate the signs (edema, erythema and excoriation) and symptoms (itching, burning and irritation) of infection, respectively, on a standardized vulvovaginal signs and symptoms scale (the Vulvovaginal Signs and Symptoms [VSS] Scale) (see [Appendix B](#)). Safety procedures, including an abbreviated physical exam, vital signs, laboratory tests and a pregnancy test will also be performed.

To be eligible for inclusion, subjects must have a minimum composite score of vulvovaginal signs and symptoms ≥ 7 with at least 2 signs or symptoms having a score of 2 (moderate) or greater in the VSS Scale, a positive KOH test and a normal vaginal pH (≤ 4.5).

Baseline (Day 1)

At the Baseline visit (which may be combined with the Screening visit), eligible subjects will be randomized in equal allocation (at a 1:1:1:1:1:1 ratio) to one of the following 6 active treatment groups (5 experimental groups and 1 active comparator group):

- Treatment Group 1: oral SCY-078 750 mg QD on Day 1 only
- Treatment Group 2: oral SCY-078 300 mg BID on Day 1 only
- Treatment Group 3: oral SCY-078 450 mg BID on Day 1 only
- Treatment Group 4: oral SCY-078 150 mg BID on Days 1 to 3
- Treatment Group 5: oral SCY-078 300 mg BID on Days 1 to 3
- Treatment Group 6: oral fluconazole 150 mg QD on Day 1 only

For the purpose of maintaining treatment blinding, all randomized subjects will receive matching SCY-078 placebo tablets and/or matching fluconazole placebo capsules as needed based on treatment assignment, in a double-dummy fashion. Study drug treatment will be dispensed on Day 1 and will be self-administered by the subjects from Day 1 (Baseline) through Day 3. Subjects will also be given subject diaries to rate their symptoms of infection on the VSS scale and to record dosing details, AEs and concomitant medication use daily from Day 1 through the TOC visit (Day 10).

Day 3

On Day 3, a PK Subset consisting of 10 subjects per treatment group (total of 60 subjects) will visit the site to have PK samples drawn pre-dose (immediately before dosing) and at 2-6 hours' post-dose of either the morning or evening dose. Day 3 will be an on-site visit for PK subjects and a phone contact visit (with a window of +3 days) for non-PK subjects. All subjects (both PK and non-PK subjects) will continue to take their assigned study treatment and rate their symptoms of infection on their subject diaries. Treatment compliance will be reviewed either on site or by phone for all subjects. Study drug may be collected from PK subjects who have completed study drug dosing at the time of this visit.

TOC (Day 10)

Vaginal samples will be obtained for local KOH testing and for fungal culture by the central laboratory. In addition, susceptibility testing will be done at the central laboratory for all positive cultures for *Candida* spp. The investigators and the subjects will rate the signs and symptoms of infection, respectively, on the VSS Scale. An abbreviated physical exam, vital sign measurements and safety laboratory tests will also be performed. Additionally, a single PK sample will be obtained at any convenient time of the day from the PK Subset only. For the PK Subset, the TOC

visit must occur as close to Day 10 as possible. All subjects will return their subject diaries. Compliance with study drug dosing will be evaluated and study drug will be collected for all subjects who did not return their study drug on Day 3.

FU (Day 25)

Vaginal samples will be obtained for local KOH testing and for fungal culture by the central laboratory. In addition, susceptibility testing will be done at the central laboratory for all positive cultures for *Candida* spp. The investigators and the subjects will rate the signs and symptoms of infection on the VSS Scale to evaluate clinical outcome.

All Visits

AEs and prior/concomitant medications will be assessed and documented at all visits.

